6.4 Study Discontinuation Criteria

Subjects MUST be discontinued from study therapy AND withdrawn from the study for the following reasons:

- Withdrawal of informed consent (subject's decision to withdraw for any reason)
- Any clinical adverse event, laboratory abnormality or intercurrent illness which, in the opinion of the Investigator/Sub-Investigator, indicates that treatment with study therapy is not in the best interest of the subject
- Pregnancy: All WOCBP should be instructed to contact the Investigator/Sub-Investigator immediately if they suspect they might be pregnant (e.g., missed or late menstrual period) at any time during study participation.
- Investigator decides to close the clinical trial prematurely.

6.5 Supportive Care Guidelines

Toxicities of the vaccination itself are expected to be minimal. For fever, acetaminophen will be utilized (325 mg tabs, 1 or 2 by mouth every 4 hours). Fevers lasting more than 8 hours after treatment will be evaluated in terms of potential infection. For mild, local pain, oral opiates will be planned (oxycodone, 5-10 mg by mouth every 3-4 hours). Pain that is of more than mild-moderate grade will be investigated for sources other than the therapy, and managed accordingly. In case of the occurrence of the acute hypersensitivity reactions, administration of IV antihistamines, corticosteroids, and epinephrine may also be required. Any cases of infection will

be treated with antibiotics, according to established guidelines.

6.6 Duration of study therapy

In the absence of treatment delays due to adverse events, treatment will continue for at least 4 doses or until one of the following criteria applies:

- Disease progression,
- Intercurrent illness that prevents further administration of treatment,
- Unacceptable adverse event(s),
- Severe reaction to the DTH testing with the tumor cell lysate prior to vaccination,
- Subject decides to withdraw from the study, or
- General or specific changes in the subject's condition rendering the subject unacceptable for further treatment in the judgment of the investigator/sub-investigator.
- Dosing delays > 4 weeks

7 STUDY EVALUATIONS AND STUDY CALENDAR

7.1 Screening

Baseline evaluations are to be conducted within 14 days prior to the leukapheresis .. Scans and x-rays must be done within six weeks prior to the start of therapy.

- Complete physical examination (with ECOG performance status (PS), weight, height, and BSA)
- Radiologic imaging to evaluate the status of disease (all scans must be obtained within 30 days of starting therapy): Includes bone scan and CT scan of chest (or CXR), abdomen, and pelvis.
- Chemistry profile including: electrolytes, creatinine, blood urea nitrogen, glucose, SGOT, SGPT, total bilirubin, calcium, and albumin.
- Serum testosterone
- PSA levels in the blood (as a tumor marker). To be eligible, subjects must have at least two PSA levels checked at least 2 weeks apart, shown to be rising, and with the the last PSA being ≥ 2.0 ng/dL
- CBC, differential, platelet
- ANA Testing (if clinically indicated)
- Known history of HIV, HbsAg, and Anti-HCV. For subjects at high risk of HIV/viral hepatitis, HIV/viral hepatitis testing will be performed to confirm status.
- Following confirmation of eligibility, based on the above tests and procedures, the following, additional pre-treatment procedures will be performed:
 - Leukapheresis – for vaccine production and a portion will be obtained for *in vitro* assays (immune parameters of CD4⁺ and CD8⁺ T cell responses against tumor-associated and tumor-irrelevant control antigens).

- DTH placement within 48-72 hours before the day of first dendritic cell vaccine administration (baseline testing) to allow for it to be read on the day of and prior to the 1st vaccine injection.

7.2 Evaluation during Treatment

During dendritic cell vaccine cycles (weeks 1, 5, 9, and 13) the following will be performed:

- Complete physical examination (with ECOG performance status and weight)
- Laboratory tests including: CBC, differential, platelet, and chemistry profile each visit (see Section 7.1 and Study Calendar).
- Blood for in vitro assays will be obtained within 1 week after each cycle of vaccination.
- PSA at week 13

7.3 Post-Treatment

- Complete history and physical examination.
- For subjects with suspected disease progression on therapy, radiographic imaging as indicated.
- PSA at week 17, 21, and every 4 weeks thereafter. Confirmatory PSA should be performed 1 month post progression
- Testosterone at week 17, 25, and every 2 months thereafter
- CBC, differential, platelets at week 25 and every 3 months thereafter
- Chemistry profile (see Section 7.1) at week 25 and every 3 months thereafter
- Blood for in vitro assays (immune parameters of CD4+ and CD8+ T cell responses against tumor-associated and tumor-irrelevant control antigens) will be obtained 1 week and 6 weeks after completion of treatment. The assays will involve the evaluation of cytokine production, cytotoxicity, and changes in cell phenotype of T cell subsets.
- Leukapheresis - a second limited leukapheresis will be performed during week 19 to facilitate immune-monitoring.
- DTH testing (post-testing: 2 to 4 weeks after last vaccine, i.e., during week 15 through 17). The subjects will be asked to agree to the biopsies being taken from the sites of the DTH tests, following their readout.
- EPIMAX analysis may be used to define the magnitude and cytokine production profiles of CD4+ and CD8+ T cell responses to the overlapping peptide libraries and individual peptides covering the entire span of PAP and PSMA molecules
- Subjects with lack of disease progression at 12 months after the last treatment may be monitored for disease free survival, as well as for overall survival.

7.4 Long Term Follow-up

Patients will continue to be followed after the last vaccine injection and/or progression based upon the timing of their standard of care for their disease.

7.5 Study Calendar

Screening evaluations are to be conducted within 14 days prior to leukapheresis. Scans and x-rays must be done within 6 weeks prior to the start of therapy.

There is a window of ± 1 week available for scheduling treatment and/or procedures at the discretion of the Investigator/Sub-investigator. This applies also if a course is missed or a subject's treatment and/or testing day(s) need to be rescheduled due to the subject's inability to comply with the study calendar (i.e., hospitalizations, business, vacation plans, travel from long distances for study treatment, in advance of the scheduled date to allow ready access to the result(s), reduce financial burden on the subject [i.e. non-UPMC insurance coverage] or reduce travel inconvenience, illness, transportation issues, holidays, family emergencies, etc.).

Parameter / Week #	Screening	Baseline	Treatment					Post-treatment						
	-4 to -1		1	3	5	9	13	14	15	16	17	19	21	25
Informed Consent	X													
History, PE, ECOG PS	X		X		X	X	X				X		X	X
Serum PSA ^g - every 4 weeks after 12 weeks of hormones	X						X				X		X	X
Serum Testosterone ^k	X										X			X
ANA testing (if clinically indicated)	X													
HIV/viral hepatitis testing	X ^f													
CT scan and Bone Scan ⁱ	X													
CBC, platelets, differential	X		X		X	X	X							X ^h
Chemistry Profile	X		X		X	X	X							X ^h
Leukapheresis (90-120 mins) ^e		X										X ^d		
Skin test (DTH)		X ^b							X ^c		X ^c			
Vaccination ^a			X		X	X	X					X ^a		
Blood (70 cc) for in vitro assays ^j			X		X	X	X							

	Screening	Baseline	Treatment					Post-treatment						
Parameter / Week #	-4 to -1		1	3	5	9	13	14	15	16	17	19	21	25
LHRH Analogue				X										

- a. Subjects may undergo additional vaccinations, every 3 months (± 1 month) if they demonstrate lack of disease progression on week 16 (or later) and if they have vaccine remaining.
- b. DTH placement should be performed within 48-72 hours prior to the day of the first dendritic cell vaccine administration to ensure the test can be read on the day and prior to the first vaccine administration.
- c. DTH testing (post-testing: within 2 – 4 weeks after last vaccine, i.e. week 15 through 17). At the discretion of the investigator/sub-investigator, subjects may be asked to agree to biopsies being taken from the sites of the DTH tests, following their readout.
- d. A second limited leukapheresis will be performed at the end of the study to facilitate immune-monitoring.
- e. EPIMAX analysis may be performed on blood samples obtained with the leukapheresis procedure.
- f. When clinically indicated, HIV/viral hepatitis testing will be performed to confirm disease status.
- g. Confirmatory PSA should be performed 1 month post progression.
- h. CBC and Chemistry profile every 3 months after week 25.
- i. Scans must be obtained within 6 weeks of starting therapy. For subjects with suspected disease progression on therapy, radiographic imaging as indicated during post-treatment.
- j. Blood for in vitro assays will be obtained within one week after each cycle of vaccination.
- k. Testosterone at week 17, 25, and every 2 months thereafter.

8 MEASUREMENT OF EFFECT

8.1 Efficacy endpoints

- The primary efficacy endpoint is to evaluate the effect of the alpha-DC1 vaccine on time to PSA progression. PSA progression is defined as a rise in the PSA value to ≥ 1.0 ng/mL.
- The secondary efficacy objectives include:
 - To determine the change in PSA velocity prior to and following the proposed treatment,
 - To estimate time to development of metastatic disease,
 - To evaluate the immunologic response to the vaccine in all subjects,
 - To evaluate the immune response to HLA-A2.1 restricted peptides derived from PAP and PSMA in subjects who are A2.1 positive,
 - EPIMAX analysis will be used to define the magnitude and cytokine production profiles of CD4⁺ and CD8⁺ T cell responses to the overlapping peptide libraries and individual peptides covering the entire span of PAP and PSMA molecules.

8.2 Safety endpoints

The primary safety endpoint is to assess the tolerability and toxicity of the alpha-DC1 vaccine.

8.3 Evaluation of Clinical Responses

The primary clinical endpoint is the time to PSA progression. Since all subjects will be treated with androgen ablation for 3 months, the expectation is that at the outset all subjects will have undetectable PSA levels. As subjects recover their testosterone levels (in 3 to 6 months), they are expected to develop a PSA relapse (5 to 7 months).

Thus time to progression (TTP) will be defined as time from starting of androgen ablation (week 2) to time of either developing *PSA progression* (see below) or the development of metastatic disease (whichever occurs sooner). Typically PSA progression will precede the development of metastatic disease.

Progressive Disease: All subjects are expected to have a PSA < 0.1 following androgen ablation. Thus PSA progression will be defined as a PSA rise of at least 1.0 ng/dL, measured at least twice, with the two values being at least 1 month apart. Changes in PSA below 1.0 ng/dL will be evaluated for the PSA slope and PSADT.

PSA Slope: The change in PSA will be graphically depicted and a PSA slope calculated. The change in PSA slope (and PSADT) pre-treatment, during treatment, and off-treatment will be determined to see if vaccine therapy has any disease modifying effects, over and above castration. This end-point is exploratory, but may lead to continued interest in this agent if the PSA slope (or PSADT) is decreased during treatment.

Clinical Progression: The appearance of new lesions on examination or radiographs (CT scan or

bone scan), or development of symptoms consistent with metastatic disease (i.e. bone pain).

Identification of Lesions: All measurements should be taken and recorded in metric notation. All baseline evaluations should be performed as closely as possible to the beginning of treatment and never more than 4 weeks before randomization. A sum of the longest diameter (LD) for all target lesions will be calculated and reported as the sum LD. The sum LD is used as reference to assess progression.

Clinical Progression free survival: This is the interval from entry to study to date of first documented lesion.

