1.2 Secondary Objectives

- To determine the change in PSA velocity prior to and following the proposed treatment.
- To evaluate (in all subjects) the vaccination-induced DTH responses to LNCap, the cell line vaccine, and to compare this with vaccination-induced responses to tumor-untreated antigen (KLH).
- To evaluate the vaccination-induced changes of Th1/Th2 profiles of the responses to PAP and PSMA.
- To evaluate the CTL responses in blood to the whole LNCap cells (in all subjects) and (in all subjects who are HLA-A2 positive) the CTL responses to HLA-A2.1 restricted peptides derived from PAP and PSMA.
- To comprehensively evaluate the CD4⁺ and CD8⁺ T cell responses (fine specificity and Th1/Th2/T_{reg} cytokine profile) to the previously-identified and novel immunogenic epitopes of PAP and PSMA, using the EPIMAX system.

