2.2 PSA Progression after Local Therapy

Patients with PSA progression after local therapy represent an ideal population for the study of novel immune approaches. Current therapy for patients with PSA progression after local therapy is unclear, and a subset of patients can be selected with greater likelihood of progression to metastatic disease, supporting the need for novel approaches. Based on recent literature, men with a PSA-doubling time (PSA-DT) of less than 10 months are at the highest risk of rapid progression and are often offered androgen ablation therapy, either on an intermittent or a continuous schedule (Gulley et al., 2005; Pound et al., 1999). However, studies have not been completed to determine a benefit of early androgen ablation therapy in patients with PSA progression after local therapy (Gulley et al., 2005). Prior studies of adjuvant androgen ablation therapy have demonstrated a benefit in only select populations of patients (Hanks et al., 2003; Lawton et al., 2001; Messing et al., 1999). Two studies demonstrated a survival benefit of adjuvant androgen ablation in concert with definitive radiation therapy in patients with locally advanced prostate cancer (Hanks et al., 2003; Lawton et al., 2001). Another study demonstrated a survival benefit to androgen ablation therapy for stage D1 disease after surgery (Messing et al., 1999).

Predictive factors for a high risk of PSA-recurrence after local therapy have also been identified. Thus Pound et al. demonstrated that time to biochemical progression, Gleason score, and PSA

doubling time were predictive of the probability and time to the development of metastatic disease (Pound et al., 1999). Recently, D'Amico et al. also demonstrated the predictive value of PSA-DT, both pre-operatively as well as after definitive local therapy (D'Amico et al., 2004). These data support using Gleason score and PSA-DT as entry criteria to select and stratify patients at high risk of disease recurrence for novel approaches to systemic therapy.

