5 STUDY DESIGN AND METHODS

This is a 2 group crossover trial in which subjects are randomly assigned to one of two treatment arms:

Cohort A: 3 months of androgen ablation (AA) to be followed at PSA progression by 3 months of the combination of AA and alpha-type 1 dendritic cell vaccine (DC1).

Cohort B: 3 months of the combination of AA and alpha-type 1 dendritic cell vaccine followed at PSA progression by 3 months of AA.

In this crossover trial each subject will serve as their own control. Following either therapy the time to PSA progression is defined as the time between treatment and the first instance of PSA increase to 1 ng/mL. The endpoint is the difference between the time to PSA progression for the combination of AA + DC1 compared to AA alone. A **total of 12 evaluable subjects** (6 subjects/arm) will be enrolled on the trial. Subjects who do not complete both courses (AA and AA+DCV) will be replaced. This schema will also help us better estimate the time to PSA recovery following 3 months of limited androgen ablation in our cohort of subjects.

All subjects in Cohort B will commence α DC1-based vaccination 2 weeks prior to treatment with the LHRH analogue. Each subject will receive 1 intradermal (*i.d.*) dose of the vaccine at weeks 1, 5, 9, and 13 for a total of 4 doses. The first dose will be considered the ‘priming’ dose and injections on weeks 5, 9, and 13 are ‘booster’ doses. Depending upon cells/volume the injections may utilize 1-2 syringes being administered on a single day. Additional courses of vaccination, if available after the 4 intended protocol doses, can be administered to any subject without evidence of disease progression, every 3 months (\pm 1 month) for up to 12 months. The schema for the vaccine can be found on page 6.

The LHRH analogue (Lupron 22.5 mg or Zoladex 10.8 mg) will be administered 2 weeks after the 1st dose of the DC vaccine.

We assume that 3 months of AA alone will be followed by PSA progression at a median of 6 months with 90% of PSA recovery times between 5 and 7 months. We suspect that a second course of AA will delay time to testosterone recovery by approximately 10% and that testosterone recovery and PSA failure will likely correlate very closely. Therefore we anticipate that a second course of AA will delay time to PSA relapse by approximately 10%. The purpose of randomizing to one of two treatment sequences is to permit an unbiased estimate of

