9.5 Data Analysis

Subjects will be required to have monthly PSA monitoring. This will enable linear interpolation between PSA samples to detect the time at which PSA progression occurs following each course of therapy. The efficacy endpoint is estimated by the difference between time to PSA progression for the AA+DCV arm and the AA arm. This difference will be tested for significance with a one tailed signed rank test. Other conventional estimates of clinical efficacy will also be calculated including PSA doubling time and PSA velocity. The PSA-DT will be calculated as follows:

The logarithm of a minimum of two PSA measurements will be plotted against the time of each PSA measurement. If 3 or more measurements are available a linear regression equation will be estimated. Two sequential PSA measurements (actual or estimated by linear regression) will be denoted as PSA1 and PSA2. Denote their times of blood samples as t1 and t2, respectively. Thus the PSA doubling time is: $\log(2)[t2 - t1] / [\log(\text{PSA}2) - \log(\text{PSA}1)]$.

Further analysis will involve testing the immunologic response of subjects receiving the α DC1-based vaccine. The principal measure of improved immunogenicity will be the comparison of pre to post α DC1-based vaccine T cell response to prostatic acid phosphatase (PAP) as measured by the IFN- γ Elispot assay. We expect that prostate cancer subjects undergoing androgen ablation in the absence of immune stimulation will have a negative or very low Elispot count for measuring reaction to PAP. Even with a nominal count of 5 spots in the group, a sample of 7 subjects with androgen ablation alone and 7 subjects treated with androgen ablation + α DC1-based vaccine will provide 90% power to detect a difference of double the Elispot count (average of 5 to 10 spots) using a one tailed alpha level Wilcoxon test if the Elispot counts have a Poisson distribution. Additional immunologic testing will be conducted by analyzing subject profiles before treatment and after each course of therapy. Immunologic endpoints include T cell reactivity by IFN γ or IL-5 Elispot, cytokine release assays for cytotoxicity and DTH tests (as measured by induration in mm). Changes over time will be tested with the Friedman Test or, if there are missing values, the Mack-Skillings procedure.

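### The exploratory PSA-kinetics criterion gives the wrong favourable direction for doubling time, and its before/during/after comparison cannot separate a vaccine effect from androgen ablation

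*Combined protocol and SAP*

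**What the plan says.** Section 8.3 plans to compute PSA slope and PSADT before, during and off treatment, looking for "disease modifying effects, over and above castration". It labels the endpoint exploratory and adds that it "may lead to continued interest in this agent if the PSA slope (or PSADT) is decreased during treatment". Just before that paragraph, it says that PSA changes below 1.0 will be assessed for slope and PSADT.

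Section 1.2 lists a related secondary objective, "To determine the change in PSA velocity prior to and following the proposed treatment", which section 8.1 repeats.

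Section 9.5 gives the formula introduced by "Thus the PSA doubling time is": log(2) times the time between two samples, divided by the difference in log PSA. Directly after the signed rank test of AA + vaccine against AA on time to PSA progression, it says "Other conventional estimates of clinical efficacy will also be calculated including PSA doubling time and PSA velocity". It names no contrast for these measures.

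Section 2.2 gives the prognostic meaning of a short doubling time: "men with a PSA-doubling time (PSA-DT) of less than 10 months are at the highest risk of rapid progression".

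On sampling, section 7.2 lists one PSA during the vaccine cycles, at week 13. The section 7.5 calendar agrees and schedules PSA "every 4 weeks after 12 weeks of hormones". The LHRH injection is at week 3.

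**The concern.** Two things go wrong if section 8.3 is followed literally.

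First, slope and doubling time are reciprocals up to a constant. While PSA is rising, a fall in one is a rise in the other, so a decrease cannot be good news for both. Section 2.2 itself treats a short doubling time as the bad state.

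Second, the stated aim is a vaccine effect beyond castration, but the comparison is each man before treatment against the same man during and after it. In the scheduled four-dose course AA starts two weeks after the first vaccine dose, and no PSA is scheduled between the two. The before/during change therefore contains the full castration response.

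At stake is how a signal of continued interest in the agent would be read. A criterion that every castrated man is expected to meet says nothing about the vaccine.

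**Working it through.** The plan gives no power, threshold or test for these measures, so there is no figure to reproduce. The check applies the plan's own formula.

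**Inputs from the protocol**
- PSADT = log(2)(t2 - t1)/(log PSA2 - log PSA1) (9.5)
- entry PSA at least 2.0 ng/mL and PSADT under 12 months (4.1; under 10 months in the Summary and section 1)
- second course started at relapse, PSA about 1.0 (Summary, 5)
- PSA expected below 0.1 after AA (8.3)
- screening at weeks -4 to -1, LHRH at week 3, PSA at week 13 (7.5)
- PSA progression at a median of 6 months after AA alone, hypothesised 7.8 months with vaccine (5)
- for the second course, "we anticipate that a second course of AA will delay time to PSA relapse by approximately 10" per cent (5)

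**Assumptions**
- PSA of 0.1 at nadir and at the start of regrowth
- the same 14 to 17 weeks from the last pre-course PSA to week 13 in either course
- 4.345 weeks per month
- regrowth linear on the scale used
- times counted from the start of AA, as in 8.3

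**1. Direction.** Log slope = ln 2/PSADT. PSADT 12 months gives 0.058 per month, 10 months gives 0.069 and 5 months gives 0.139. A doubling time that decreases from 10 to 5 months means the slope has doubled. Halving the slope from a PSADT of 10 lengthens it to 20.

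**2. During treatment, no vaccine effect.** The interval is 14/4.345 = 3.22 to 17/4.345 = 3.91 months.

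| PSA before the course | ln(0.1/PSA) | log slope per month | formula PSADT, months |
|---|---|---|---|
| 1.0 (cohort A, vaccine course) | -2.303 | -0.59 to -0.72 | -1.18 to -0.97 |
| 2.0 (entry minimum) | -2.996 | -0.77 to -0.93 | -0.91 to -0.75 |

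The slope before treatment is positive: at least 0.058 at entry, and positive by definition at relapse. A higher entry PSA or a nadir below 0.1 makes the on-treatment slope more negative. The negative PSADT values are not doubling times, and they order the wrong way: the slower fall from 2.0 gives the lower number (-0.91 against -0.75).

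**3. Off treatment and the before/after velocity.** After AA alone, PSA goes from 0.1 to 1.0 by month 6. If regrowth starts at month s, velocity is 0.9/(6 - s): 0.30, 0.45 and 0.90 ng/mL per month for s = 3, 4 and 5. Pre-treatment velocity is PSA x ln 2/PSADT. With PSADT 10, that is 0.139 at PSA 2.0 and 0.693 at an assumed PSA of 10. The after/before ratios are 2.2, 3.2 and 6.5 in the first case, and 0.43, 0.65 and 1.30 in the second. The size, and sometimes the direction, depends on entry PSA and on when testosterone recovers.

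**4. What a between-course contrast would show.** Regrowth log slope = ln(10)/(T - s). With s = 3:
- T = 6: 0.768
- T = 6 x 1.1 = 6.6: 0.640
- T = 7.8: 0.480
- T = 7.8 x 1.1 = 8.58: 0.413

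AA + vaccine minus AA:
- No vaccine effect: cohort A 0.640 - 0.768 = -0.13; cohort B 0.768 - 0.640 = +0.13; equal-weight mean 0.
- Hypothesised 30% delay: cohort A 0.413 - 0.768 = -0.36; cohort B 0.480 - 0.640 = -0.16; mean -0.26 (-0.46 with s = 4).

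The crossover therefore removes castration from the comparison, and equal weighting cancels the assumed second-course delay.

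**The case against.** The endpoint is called exploratory, has no threshold or test, and only may prompt further interest. That stands, and it keeps the point minor.

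A between-course comparison may be what was meant. Sections 3 and 5 make each man his own control, and section 9.5 mentions PSADT and velocity straight after the AA + vaccine versus AA test. This is plausible, but the between-course difference is written only for time to PSA progression. Section 8.3 writes a different comparison for slope and PSADT.

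Section 8.3 also points to PSA below 1.0, which suggests the regrowth phase rather than the initial fall. That is a fair reading and the fix builds on it. It does not repair the criterion, which speaks of a decrease during treatment relative to before.

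A reader might infer that vaccine is never given without AA, so that no vaccine-only period exists. The documents do not support that. The Summary and sections 5, 6.2 and 7.5 allow further vaccine doses about every 3 months in men without progression, while the calendar shows a single LHRH injection. PSA is drawn every 4 weeks in that period. Slopes there are still confounded, because testosterone is recovering.

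Section 9.5 requires monthly PSA, more than the calendar shows during vaccination. Additional on-treatment values would record the same castration response.

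**Conclusion.** The point holds and is minor. For a rising PSA the direction stated for PSADT is wrong by the plan's own formula and its own account of prognosis. For a falling PSA the quantity is not interpretable. The before/during comparison is expected to show a lower slope in every man from AA alone: about -0.6 to -0.7 per month starting from PSA 1.0 and -0.8 to -0.9 from 2.0, against a positive slope beforehand. The before/after velocity objective has the same weakness.

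The direction error needs no assumption beyond the formula. The slopes rest on PSA reaching 0.1 by week 13 and on the calendar intervals. The contrast figures also assume a fixed start of regrowth and a vaccine that slows regrowth.

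It would be wrong to infer that the trial cannot separate vaccine from castration, or that its main efficacy result is compromised. Every man who completes both courses has an AA-alone course, and the primary test of time to PSA progression already uses it.

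**What to change.** In sections 8.3 and 9.5:

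- State the favourable direction as a lower log-PSA slope or a longer PSADT, computed only from detectable, rising PSA values after nadir (the below-1.0 phase that 8.3 already names). Do not compute PSADT from falling or undetectable values.
- Define the exploratory contrast as the within-subject difference in that regrowth slope, AA + vaccine course minus AA-alone course, over the same window from each LHRH injection.
- Report it by cohort and as the equal-weight mean of the two cohorts, because of the assumed second-course delay.
- Flag men who received additional vaccine doses inside the window, and note that vaccine carry-over into cohort B's AA course could dilute the contrast.
- Keep pre- versus on-treatment slopes, and the before/after velocity of sections 1.2 and 8.1, as description only.

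The cost is wording and one named contrast on PSA values already scheduled. The limits should be stated: heavy overlap with the primary endpoint (in the illustration the slope is a direct function of progression time), few detectable values per course, and low sensitivity if the vaccine delays the onset of regrowth without slowing it.
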